8.1.2.5 Pharmacokinetic (PK) Population

All subjects in the Safety population who receive at least 1 dose of GE-IR, and have at least 1 PK concentration after dosing will be included in the PK population.

8.2 Appropriateness of Measures

The selected PD measures will assess positive and negative subjective drug effects associated with the abuse potential of this drug. These subjective measures are consistent with guidelines for HAP studies⁴ and are similar to those used in previous studies. Although data from all measures will be considered in the assessment of abuse potential, the Drug Liking VAS has been selected as the primary endpoint for practical purposes (such as calculating power and assessing qualification eligibility), as it is considered 1 of the most sensitive and face-valid measures of abuse potential.^{6,7} Overall Drug Liking VAS and Take Drug Again VAS have been selected as key secondary endpoints as they represent the subject's global assessment of the drug and have face validity for predicting continued use of a drug. High VAS has also been selected as a key secondary endpoint because it has been shown to be sensitive in capturing the positive subjective effects of test drugs. Additional secondary endpoints assess other subjective effects of the drug that may help with interpretation of the data.

Standard PK parameters will be evaluated to confirm plasma concentrations and the PK profile of GE-IR in the PK population. Standard measures of safety will be included to monitor the safety and tolerability of the GE-IR doses used in the study.

8.3 Missing Values

No imputation of missing PD or PK data will be performed.

The occurrence of missing PD data will be minimized by only including subjects who are rousable and complete PD assessments in the Qualification phase. In addition, all reasonable attempts will be made to rouse subjects for completion of the PD assessments in both the Qualification and Treatment phases. Missing PD assessments, including reasons for the missing data, will be listed by subject, and examined on a case-by-case basis to determine if these affect subject allocation (i.e., inclusion in the Modified Completer population). If for a given PD measure, the predose value is missing, calculation of CFB_{min} and TA_AOE will not be possible, and the subject will not be included in the Modified Completer population for that PD endpoint. If the actual date and/or time of a postdose PD assessment is unknown, but there is a result at that timepoint, the value will be used in descriptive statistics of treatment by timepoint summaries, and PD endpoint by treatment summaries but will be excluded from calculation of TA_AUE and TA_AOE which need actual time from dose in order to be calculated.

If the actual collection time of a postdose PK sample is unknown, but a valid concentration value has been measured, the sample will be set to missing in the PK analysis and will be presented in

listing but excluded from descriptive statistics. Unknown baseline collection times will be handled on a case-by-case basis.

Further details on handling of missing values will be provided in the Subject Allocation and Request to Break the Blind Form, and in the Statistical Analysis Plan (SAP).

8.4 Demographic Data and Other Baseline Characteristics

8.4.1 Qualification Phase

All subjects who are randomized into the qualification phase will be entered into the database. Disposition tables and listings will be presented for all subjects in the Qualification Randomized population. Demographics and baseline characteristics (sex, age, race, ethnicity, body weight, height, BMI) will be summarized for the Qualification Safety population. Qualification passes and failures will be listed separately.

8.4.2 Treatment Phase

A disposition table will be presented for all subjects randomized to the Treatment phase. Demographics and baseline characteristics (sex, age, race, ethnicity, body weight, height, BMI), recreational drug use history, alcohol use history, and smoking history will be summarized using descriptive statistics (n, mean, SD, minimum, median, and maximum for continuous variables, and the proportion of subjects for categorical variables) for the Safety population. No formal statistical comparison between the groups will be performed.

Medical history will be listed by subject. Medical history will be coded into the most recent version of MedDRA available (version 22.0 or later).

Prior and concomitant medications will be assigned a 12-digit code using the most recent version of the World Health Organization drug codes available. Prior and concomitant medications will be listed by subject.

The number of subjects in each treatment group will be presented, in addition to the number of subjects who complete each treatment period. The reasons for all post-randomization discontinuations will be tabulated and grouped by treatment and major reason. All deviations related to study inclusion or exclusion criteria, conduct of the trial, subject management, or subject assessment will be listed.

8.5 Pharmacodynamics

8.5.1 Pharmacodynamic Endpoints

Pharmacodynamic endpoints will be evaluated as described in [Table 7](#) and all PD data will be analyzed using the Modified Completer population.

Table 7. Pharmacodynamic Endpoints

Description	Type	Endpoints
Drug Liking	Bipolar VAS	E_{max} , E_{min} , TE_{max} , TE_{min} , and TA_AUE
Overall Drug Liking	Bipolar VAS	E_{max}
Take Drug Again	Bipolar VAS	E_{max}
High	Unipolar VAS	E_{max} , TE_{max} , and TA_AUE
Good Effects	Unipolar VAS	E_{max} , TE_{max} , and TA_AUE
Bad Effects	Unipolar VAS	E_{max} , TE_{max} , and TA_AUE
Any Effects	Unipolar VAS	E_{max} , TE_{max} , and TA_AUE
Feeling Drunk	Unipolar VAS	E_{max} , TE_{max} , and TA_AUE
Drowsiness/Alertness	Bipolar VAS	E_{min} , TE_{min} , and TA_AOE
Relaxation/Agitation	Bipolar VAS	E_{min} , TE_{min} , and TA_AOE
Addiction Research Center Inventory (ARCI) Morphine- Benzedrine Group (MBG) Scale	Questionnaire score	E_{max} , TE_{max} , and TA_AUE
ACRI Pentobarbital- Chlorpromazine-Alcohol Group (PCAG) Scale	Questionnaire score	E_{max} , TE_{max} , and TA_AUE
Modified Observer's Assessment of Alertness/Sedation (MOAA/S)	Observer's score	E_{min} , CFB_{min} , and TA_AOE

CFB_{min} = change from baseline to minimum effect, E_{max} = maximum (peak) effect, E_{min} =minimum effect, TA_AOE= time-averaged area over the effect-time curve, TA_AUE=time-averaged area under the effect-time curve, TE_{max} =time of maximum (peak) effect, TE_{min} =time of minimum effect, VAS=Visual Analog Scale

8.5.2 Pharmacodynamic Statistical Methodology

Drug Liking and Take Drug Again VAS E_{max} from the Qualification phase will be summarized by treatment and paired difference for the Modified Completer population. The data will be evaluated to confirm that an appropriate population was selected for the Treatment phase.

During the Treatment phase, PD values at each timepoint will be summarized by treatment using descriptive statistics and presented graphically. Derived endpoints will be summarized by treatment and paired difference using descriptive statistics.

8.5.2.1 Primary Analysis

Pharmacodynamic endpoints for the Treatment phase (E_{max} , E_{min} , CFB_{min} , TA_AUE and TA_AOE, as appropriate) will be analyzed using a mixed-effect model if the residuals are normally distributed. The model will include treatment, period, treatment sequence, and first-order carryover effect (where applicable) as fixed effects, and the baseline (predose) measurement as a covariate (where applicable). If the variance among treatments is homogeneous, subject will be considered a random effect; if the variance among treatments is heterogeneous, the default variance components (VC) variance structure block will be used for

each subject. Treatments for each PD endpoint will be tested for homogeneity of variance using

[REDACTED]

[REDACTED]

[REDACTED]

[REDACTED]

[REDACTED]

After it is determined if the treatment variance is homogeneous or heterogeneous, the residuals from each mixed-effect model will be investigated for normality using the Shapiro-Wilk W test. The null and alternative hypotheses for this analysis are shown below:

H_0 : distribution of residuals is normal vs. H_a : distribution of residuals is not normal

If the residuals from the mixed-effect model are normally distributed, e.g., $p\text{-value} \geq 0.05$, it will be determined if carryover effects should be included.

When conducting drug abuse potential studies, Chen and Tsong¹⁴ have recommended the inclusion of first-order carryover as a fixed effect in the mixed-effect model. The adoption of this conservative approach would address possible effects associated with the subjective nature of these studies. Carryover effects are defined as the treatment administered in the previous treatment period. As there are no carryover effects in treatment period 1, placebo will be used in this period. If the carryover effect is found to be non-significant at $\alpha \geq 0.25$, then the term will be dropped from the mixed-effects model. If the carryover effect is found to be significant at $\alpha < 0.25$, it will be included in the model.

If the normality assumption of the model is satisfied, least-square means, standard errors (SEs), and 1-sided 95% or 2-sided 95% or 90% confidence intervals (CIs) for treatments and treatment differences will be derived from the mixed-effect model. P-values will be provided for the effects and the contrasts.

8.5.2.1.1 Test Hypotheses for Primary Endpoint, Drug Liking VAS E_{max}

The primary objective of a HAP study is to provide information on the relative abuse potential of a test drug in humans.⁴ The statistical analysis of a HAP study should address the following questions:

1. Does the known drug of abuse (positive control) produce reliable abuse-related responses compared to placebo (study validity)?
2. Does the test drug produce abuse-related responses that are smaller than those of the positive control?
3. Does the test drug produce abuse-related responses that are similar to placebo?

To address these issues, the following hypotheses will be tested for Drug Liking VAS E_{max} at a significance level of 0.05; 1-sided 95% confidence intervals will be used.

These hypotheses will be applied to the primary endpoint, Drug Liking VAS E_{max} .

Although a margin of 15 has been selected for Hypothesis 1 to ensure consistency with the Qualification phase criteria, subjects are expected to provide lower responses in the Treatment phase as compared to the Qualification phase.^{19,31} Therefore, if the difference between the positive control and placebo does not meet the recommended criterion for validity (i.e., $\delta_1=15$), a secondary planned analysis will be performed (refer to section 8.5.2.2) A margin of 11 points is considered appropriate for Hypothesis 3 based on an analysis of Drug Liking VAS E_{max} data.¹⁵ Further details will be described in the SAP..

For study validity purposes, the primary endpoint, E_{max} for Drug Liking VAS, will be compared between the positive control (alprazolam 2 mg) and placebo. [REDACTED]

[REDACTED] If statistically significant, it will confirm the sensitivity of the study and allow for the comparison of the other pairwise comparisons shown below. The hypotheses can be expressed as follows:

[REDACTED]

where μ_C is the mean for the positive control, alprazolam, and μ_P is the mean for placebo, and will be applied to the following contrast:

[REDACTED]

To assess whether the test drug has less abuse potential than the positive control, the null hypothesis will be that the mean difference in Drug Liking E_{max} between alprazolam and GE-IR is less than or equal to 0 against the alternative hypothesis that the mean difference in Drug Liking E_{max} between alprazolam and GE-IR is greater than 0.

Comparison between the positive control, alprazolam, and the test drug, GE-IR, will be:

[REDACTED] [REDACTED] [REDACTED] [REDACTED] [REDACTED] [REDACTED] [REDACTED]

where μ_C is the mean for the positive control, alprazolam, and μ_T is the mean for the test drug, GE-IR, and will be applied to the following contrasts:

- [REDACTED]
- [REDACTED]
- [REDACTED]

To assess whether the test drug, GE-IR, shows similar abuse potential to placebo, the hypothesis for the comparison will be:

[REDACTED] [REDACTED] [REDACTED] [REDACTED] [REDACTED] [REDACTED] [REDACTED]

where μ_T is the mean for the test drug, GE-IR, and μ_P is the mean for placebo, and will be applied to the following contrasts:

- [REDACTED]
- [REDACTED]
- [REDACTED]

8.5.2.1.2 Test Hypotheses for Key Secondary Endpoints

The key secondary endpoints in this study will be E_{max} of Overall Drug Liking, Take Drug Again and High. For the comparisons of key secondary PD endpoints, the following hypothesis will be used to provide information on the relative abuse potential of the test drug in humans:

[REDACTED] [REDACTED] [REDACTED] [REDACTED] [REDACTED] [REDACTED] [REDACTED]
[REDACTED] [REDACTED] [REDACTED] [REDACTED] [REDACTED] [REDACTED] [REDACTED]
[REDACTED] [REDACTED] [REDACTED] [REDACTED] [REDACTED] [REDACTED] [REDACTED]

The hypothesis for comparison between the positive control, alprazolam and placebo will be:

[REDACTED] [REDACTED] [REDACTED] [REDACTED] [REDACTED] [REDACTED] [REDACTED]

where μ_C is the mean for the positive control, alprazolam, and μ_P is the mean for placebo, and will be applied to the following contrast:

■ [REDACTED]

The hypothesis for comparison between the positive comparator, alprazolam, and the test drug, GE-IR, will be:

[REDACTED]

[REDACTED]

where μ_C is the mean for the positive control, alprazolam, and μ_T is the mean for the test drug, GE-IR, and will be applied to the following contrasts:

[REDACTED]

The hypothesis for comparison between the test drug, GE-IR, and placebo will be:

[REDACTED]

[REDACTED]

where μ_T is the mean for the test drug, GE-IR, and μ_P is the mean for placebo, and will be applied to the following contrasts:

[REDACTED]
[REDACTED]
[REDACTED]

A significance level of 0.05 will be used for all 1-sided tests; 1-sided 95% confidence intervals will be presented. For 2-sided tests, a significance level of 0.1 will be used ³² with 2-sided 90% confidence intervals. No adjustments for p-values will be made to account for multiple comparisons.

8.5.2.1.3 Test Hypotheses for Non-Key Secondary Endpoints

For the comparisons of all other non-key secondary PD endpoints, the following hypothesis will be used to provide information on the relative abuse potential of the test drug in humans:

[REDACTED]
[REDACTED]
[REDACTED]

The hypothesis for comparison between the positive control, alprazolam and placebo will be:

[REDACTED] [REDACTED]

where μ_C is the mean for the positive control, alprazolam, and μ_P is the mean for placebo, and will be applied to the following contrast:

[REDACTED]

The hypothesis for comparison between the positive comparator, alprazolam, and the test drug, GE-IR, will be:

[REDACTED] [REDACTED]

where μ_C is the mean for the positive control, alprazolam, and μ_T is the mean for the test drug, GE-IR, and will be applied to the following contrasts:

[REDACTED]
[REDACTED]
[REDACTED]

The hypothesis for comparison between the test drug, GE-IR, and placebo will be:

[REDACTED] [REDACTED]

where μ_T is the mean for the test drug, GE-IR, and μ_P is the mean for placebo, and will be applied to the following contrasts:

[REDACTED]
[REDACTED]
[REDACTED]

A significance level of 0.05 will be used for Hypotheses 1 and 2, and a significance level of 0.1 will be used for Hypothesis 3.³² For Hypotheses 1 and 2, 2-sided 95% confidence intervals will be presented while 2-sided 90% confidence intervals will be presented for Hypothesis 3. No adjustments for p-values will be made to account for multiple comparisons.

8.5.2.2 Secondary Analysis

Although a margin of 15 has been selected for Hypothesis 1 for consistency with the Qualification phase criteria, subjects may have lower responses with alprazolam and higher responses with placebo in the Treatment phase as compared to the Qualification phase,^{19,31} particularly for lower abuse potential drugs such as benzodiazepines (i.e., Schedule IV drugs). Therefore, in the case that the difference between the active control and placebo does not meet

the pre-specified criteria for validity of at least 15 points, secondary analysis will be performed. Details of the secondary analysis will be described in the SAP.

8.6 Pharmacokinetics

The PK analysis will be carried out according to Altasciences SOPs. Pharmacokinetic data handling and analysis will be further detailed in the SAP.

8.6.1 Measurements Below the Lower Limit of Quantitation

Concentration values below the lower limit of quantitation (LLOQ) associated with predose and postdose collection times will be replaced with zero for the non-compartmental analyses (NCA).

Concentration values below the LLOQ will be replaced with 0 for mean PK profile representations as well as for descriptive statistic calculations.

8.6.2 Actual Time

Analysis will be based on the actual sampling times, except for predose samples, which will always be reported as 0, regardless of time deviations.

The individual concentration/time profiles will be presented using actual sampling times whereas the mean concentration/time profiles and tables presenting summary statistics of concentration-time series will be presented using nominal sampling times.

Actual times will be listed in the report.

8.6.3 Noncompartmental Analysis (NCA)

The following configuration for the NCA analysis (with Phoenix® WinNonlin® version 8, or higher) will be used:

Reason for exclusion of AUC: In the case where less than 3 consecutive measurable concentrations are observed, the AUC parameters will not be estimated.

The PK parameters for gabapentin are presented in [Table 8](#).

Table 8. Pharmacokinetic Parameters

Parameter	Definition
C_{\max}	Maximum observed concentration occurring at time T_{\max}
T_{\max}	Time of maximum observed concentration. If the maximum observed concentration is not unique, then the first maximum is used.
AUC_{0-T}	Area under the concentration time curve from the time 0 to T_{last} .
T_{last}	Time of last measurable (positive) observed concentration

8.6.4 Pharmacokinetic Statistical Methodology

8.6.4.1 Descriptive Statistics

Descriptive statistics of the individual concentration data and derived parameters will be calculated with the build-in Phoenix® WinNonlin® platform and displayed with the same precision as received from the bioanalytical laboratory.

Precision for individual values will be display as follows:

- C_{\max} and AUC will be displayed with the same precision as the raw PK concentration data
- Parameters associated with time will be displayed with 2 decimal places

Summary statistics will be displayed with the same precision as the individual values, with the exception of number of observations (N) and coefficient of variation (CV%) which will be presented with 0 and 1 decimal place, respectively.

Descriptive statistics will be calculated for concentrations at each individual timepoint and for all PK parameters. Individual concentrations, and PK parameters obtained from the NCA will be summarized per treatment group using the following descriptive statistics: N, minimum, arithmetic mean, geometric mean, median, maximum, standard deviation (SD), CV%.

8.6.4.2 Statistical Analysis

No formal statistical analysis of PK data will be performed.

8.7 Safety

8.7.1 Safety Endpoints

For the Treatment phase, safety endpoints will include a summary of the incidence of AEs, SAEs, as well as descriptive summary and statistics of the safety parameters (clinical laboratory values, vital signs [i.e., systolic and diastolic blood pressure, pulse rate, respiratory rate, oral temperature, SpO₂], continuous SpO₂ monitoring, continuous EtCO₂ monitoring, ECGs, C-SSRS, and physical examination findings.

8.7.2 Safety Analysis

The clinical laboratory tests and the measurements of vital signs, continuous SpO₂ and EtCO₂ monitoring, ECGs, C-SSRS and physical examination parameters will be used to perform the safety statistical analysis.

8.7.3 Safety Statistical Methodology

8.7.3.1 Qualification Phase

The Qualification Randomized population will be used to list all AEs occurring in the Qualification phase. Qualification passes and failures will be listed separately.

8.7.3.2 Treatment Phase

Analysis of safety assessments will be performed using the Safety population. Assessment of safety will be based on the incidence of AEs, AEs resulting in discontinuation, and SAEs by treatment. AE summaries will be provided showing the number and percentage of subjects who experienced at least 1 TEAE during the Treatment phase. TEAEs will also be tabulated by maximum severity and by maximum relationship to study drug. These summaries will be presented by body system and preferred term (Medical Dictionary for Regulatory Activities [MedDRA], version 22.0 or higher). SAEs and AEs resulting in discontinuation will be summarized separately. All AEs will be listed by subject for the Safety population.

Laboratory data collected during the Treatment phase will be summarized by the type of laboratory test and visit. Descriptive statistics (n, mean, SD, minimum, median, and maximum) and the number of subjects with laboratory test results below, within, and above normal ranges will be tabulated by visit. Abnormal findings in laboratory data will be listed.

Treatment phase vital signs (blood pressure, heart rate, respiratory rate, SpO₂) and EtCO₂ will be analyzed as minimum, maximum, and final postdose values since the analyses of these extremes are more meaningful than analyses of individual timepoints. Vital signs will be summarized using descriptive statistics (n, mean, SD, minimum, median, and maximum). Abnormal findings in vital signs data will be listed.

12-Lead ECG data during the Treatment phase (absolute values in heart rate and PR, QRS, QT, and QTcF intervals) will be summarized by parameter and visit using descriptive statistics (n, mean, SD, minimum, median, and maximum). Overall ECG interpretation will be summarized (normal; abnormal, non-clinically significant; and abnormal, clinically significant). Abnormal findings in ECG data will be listed.

Physical examination abnormal results will be listed by subject and visit. Baseline and since last visit scores from the C-SSRS questionnaire will be listed. No summaries will be provided.

8.8 Planned Interim Analyses

No formal interim analyses will be performed.

8.9 Determination of Sample Size

As reported in an unpublished HAP study evaluating doses of 1.5 mg and 3.0 mg of alprazolam, the mean paired difference (SD) for Drug Liking VAS E_{max} VAS between alprazolam 1.5 mg and placebo was 26.3 (18.62). For alprazolam 3.0 mg vs. placebo, the mean difference (SD) was 26.6 (17.83). A margin of 15, with a correlation of 0, and an upper-tailed test with a significance level of 0.05 results in 48 completers for the comparison of alprazolam 1.5 mg vs. placebo, and 42 completers for the comparison alprazolam 3.0 mg vs. placebo. The more conservative sample size estimate of 48 subjects will be used.

Assuming a drop-out rate of approximately 25%, and allowing for missed data and problematic subjects as defined for the Modified Completer population, approximately 60 subjects are planned for randomization into the Treatment phase in order to achieve a minimum of 48 completers (at least 4 subjects per 10 treatment sequences).

Due to potential sedative effects that may prevent subjects from completing measures and expected natural attrition, replacement subjects may be considered in order to meet the minimum number of completers, in the event that the preplanned attrition rate of 25% is surpassed.

Subjects will be consecutively randomized into the Qualification phase until the target number of 60 subjects eligible for participation in the Treatment phase is reached.

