Placebo, Dose, and Mode of Administration:	
Placebo-to-match GE-IR capsules Manufacturer: Arbor Pharmaceuticals, LLC Mode of administration: Single doses of placebo-to-match GE-IR (233.3 mg

	
over-encapsulated placebo) capsule in one Swedish Orange Opaque AAEL-DB capsule) capsule(s) will be administered orally according to the randomization schedule during the Treatment phase.
 
Over-encapsulated placebo-to-match alprazolam
 
Mode of administration: Single doses of placebo-to-match alprazolam (2 × over-encapsulated placebo tablets in one Swedish Orange Opaque AAEL-DB capsule) will be administered orally according to the randomization schedule during the Qualification and Treatment phases.

Study Design:	
This study will be a randomized, double-blind, active- and placebo-controlled, 5-way crossover study to determine the abuse potential of GE-IR relative to alprazolam and placebo, in nondependent, recreational drug users with sedative drug use experience.
 
This study will consist of 3 phases: screening, qualification and treatment.

Duration of Treatment and Subject Confinement:	
Duration of clinical trial (per subject):
 
Screening: Day -30 to Day -2
 
Qualification phase: Subjects will be confined to the clinical site from Day -1 until Day 4. A minimum 3-day washout will be required between the last dose in the Qualification phase and the first dose of the Treatment phase.
 
Treatment phase: Subjects will be confined to the clinical site from Treatment phase Day -1 until Day 14.
 
Total study duration: up to approximately 49 days (including screening)

Study Population:	Healthy, male and female nondependent, recreational drug users with sedative drug experience, aged 18 to 55 years.
Planned Number of Subjects:	Approximately 60 subjects will be randomized into the Treatment phase, such that approximately 48 subjects complete the Treatment phase of the study.
Bioanalysis:	Gabapentin plasma concentrations will be measured by a validated bioanalytical method.
Pharmacodynamic Analysis:	For each PD endpoint, descriptive statistics by treatment and paired difference, and inferential analysis using a mixed-effects model, a paired t-test or the sign test, as appropriate, will be performed.
Pharmacokinetic Analysis:	PK analyses will be performed by non-compartmental analysis (NCA) and C_{max} , T_{max} , T_{last} , and AUC_{0-T} will be estimated for gabapentin.

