5.2.3 Method of Assigning Subjects to Treatment Groups

The designated, unblinded biostatistician will generate the separate randomization codes for the Qualification and Treatment phases with a computer program according to the study design, the number of subjects and the sequence of treatment administration. For the Qualification and Treatment phases, the random allocation of each sequence of treatment administration to each subject will be done in such a way that the study is balanced. Once generated, the randomization codes will be final and will not be modified.

Subjects who sign the ICF and are randomized but do not receive a study treatment in the Treatment phase may be replaced. Subjects who sign the ICF, are randomized and receive a study treatment in the Treatment phase, and subsequently withdraw, or are withdrawn or discontinued from the study, may be replaced.

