5.2.4 Blinding

The treatment assignment will not be known by the study subjects.

Furthermore, the randomization code will not be available to investigators and clinical staff involved in the collection, monitoring, revision, or evaluation of AEs, as well as clinical staff that could have an impact on the outcome of the study, including the biostatistician and pharmacokineticist (or delegate). When all PD assessments during the Qualification phase have been completed for each cohort, the randomization will be released to allow for the evaluation of qualification criteria. For the Treatment phase, the randomization will remain blinded until all the CRFs have been approved and signed.

The preparation and/or dispensing of the products will be performed by designated personnel that are not directly involved in the clinical aspects of the trial.

The randomization code must not be broken except in emergency situations where the identification of a subject's study treatment is required by an investigator for further treatment of the subject or by the designated unblinding person(s) in the case of a suspected, unexpected SAE (SUSAR) report. Randomization information will be held by designated individual(s). The date and reason for breaking the blind must be recorded.

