### 3.3 Determination of Sample Size

As reported in an unpublished human abuse potential (HAP) study evaluating doses of 1.5 mg and 3.0 mg of alprazolam, the mean paired difference (SD) for Drug Liking VAS  $E_{max}$  VAS between alprazolam 1.5 mg and placebo was 26.3 (18.62). For alprazolam 3.0 mg vs. placebo, the mean difference (SD) was 26.6 (17.83). A margin of 15, with a correlation of 0, and an upper-tailed test with a significance level of 0.05 results in 48 completers for the comparison of alprazolam 1.5 mg vs. placebo, and 42 completers for the comparison alprazolam 3.0 mg vs. placebo. The more conservative sample size estimate of 48 subjects will be used.

Assuming a drop-out rate of approximately 25%, and allowing for missed data and problematic subjects as defined for the Modified Completer population, approximately 60 subjects are planned for randomization into the treatment phase in order to achieve a minimum of 48 completers (at least 4 subjects per 10 treatment sequences).

Due to potential sedative effects that may prevent subjects from completing measures and expected natural attrition, replacement subjects may be considered in order to meet the minimum number of completers, in the event that the preplanned attrition rate of 25% is surpassed.

Subjects will be consecutively randomized into the qualification phase until the target number of 60 subjects eligible for participation in the treatment phase is reached.

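### Sixty randomized at the stated 25% drop-out leave 45 completers, not the stated minimum of 48, and the 25% replacement trigger comes after 48 is already lost

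*Protocol*

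**What the plan says.** Protocol 8.9 first derives 48 completers from the comparison of alprazolam with placebo. It then sets the number to randomize: "Assuming a drop-out rate of approximately 25"%, and "allowing for missed data and problematic subjects as defined for the Modified Completer population", it concludes that "approximately 60 subjects are planned for randomization into the Treatment phase in order to achieve a minimum of 48 completers". SAP 3.3 repeats the reasoning with the same figures ("Assuming a drop-out rate of approximately 25%, and allowing for missed data and problematic subjects as defined for the Modified Completer population").

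On replacement, both sections say that extra subjects may be considered, for the purpose of meeting the minimum number of completers, "in the event that the preplanned attrition rate of 25% is surpassed".

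Protocol 5.2.3 and SAP 3.5.1 deal with replacement separately and attach no threshold. Subjects who have been dosed in the Treatment phase and "subsequently withdraw, or are withdrawn or discontinued from the study, may be replaced".

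The synopsis words the target more loosely than 8.9: about 60 are to be randomized such that "approximately 48 subjects complete the Treatment phase of the study".

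**The concern.** A drop-out rate is a fraction of those randomized. Taking 25% from 60 leaves fewer than 48, so the stated minimum does not follow from the stated assumption. The 60 looks like 48 increased by 25%, where the calculation should have divided 48 by 0.75.

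The same 25% then serves as the replacement trigger. A trigger meant to protect 48 completers should act when 48 is threatened, yet this one acts only after 48 is out of reach. Between those two points section 8.9 gives no ground for replacement, while 5.2.3 permits it without condition. Site staff and sponsor could decide differently at 13 to 15 losses depending on which section they read. At stake are the stated minimum and a usable replacement rule. The power of the trial is little affected.

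**Working it through.** **Inputs** (protocol 8.9, same in SAP 3.3): 60 randomized; 25% drop-out; minimum of 48 completers; replacement when attrition exceeds 25%; mean differences (SD) of 26.3 (18.62) for alprazolam 1.5 mg and 26.6 (17.83) for 3.0 mg against placebo; margin 15; correlation 0; one-sided 0.05. No power is stated.

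**1. Reproducing the 48.** One-sample (paired) t-test with the noncentral t distribution:
- 1.5 mg: effect beyond the margin 26.3 − 15 = 11.3; SD 18.62 × √2 = 26.33; 90% power needs 48.
- 3.0 mg: 26.6 − 15 = 11.6; SD 17.83 × √2 = 25.22; 90% power needs 42.

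Both stated figures come out exactly, so 90% power and the √2 factor for correlation 0 are inferred to be the plan's basis.

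**2. From 48 to 60.**
- Forward: 60 × (1 − 0.25) = 45, which is 3 short of 48.
- Backward: 48/(1 − 0.25) = 64, not 60.
- Sources of 60: 48 × 1.25 = 60, or 48/(1 − 0.20) = 60.
- Largest loss that 60 can bear: 1 − 48/60 = 20%, or 12 subjects.

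The plan's figure does not reproduce at 25%.

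**3. The replacement trigger.** 25% of 60 is 15, so attrition first exceeds 25% at 16 losses.

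| Losses of 60 | Rate | Completers left | 48 kept? | 8.9 trigger reached? |
|---|---|---|---|---|
| 12 | 20.0% | 48 | yes | no |
| 13 | 21.7% | 47 | no | no |
| 14 | 23.3% | 46 | no | no |
| 15 | 25.0% | 45 | no | no |
| 16 | 26.7% | 44 | no | yes |

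**4. How often this would arise.** Assume that each of 60 subjects drops out independently and none is replaced.
- At 25%: P(13 or more losses) = 0.768; P(13 to 15) = 0.337; P(16 or more) = 0.431.
- At 20%: P(13 or more losses) = 0.424.

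**5. Effect on power for alprazolam against placebo** (effect 11.3 beyond the margin, one-sided 0.05):
- SD 18.62 × √2: 90.1% at 48 completers, 88.3% at 45.
- SD 18.62, taken as already the SD of the paired difference: 99.4% at 48, 99.1% at 45.

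**The case against.** Four points can be made for the plan.

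*The 25% may mean 12 extra per 48 completers.* On that reading 60, 48 and the trigger agree, because passing 25% would mean more than 12 losses. But a drop-out or attrition rate of randomized subjects has the number randomized as its denominator, and neither document says otherwise. If this was the intention, the text still has to change, and the rate to state is 20%.

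*Replacement is permitted anyway.* Both rules are permissive, 8.9 does not say that replacement may happen only above 25%, and 5.2.3 has no threshold. This stands in part: 48 can be reached, and nothing forbids replacement at 13 losses. It does not correct 8.9, which attaches a condition that 5.2.3 lacks and that comes too late for its own purpose. It also means that the probabilities in step 4 describe the plan before any replacement, not the expected final count.

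*The consequence is small.* This stands. Forty-five exceeds the 42 derived from the 3.0 mg data and the 40 implied by four subjects in each of ten sequences, and the loss of power is under two percentage points.

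*Restating 20% fits the assumption to the number.* No passage supports 20% as a forecast. That is fair, and is why the fix also offers the wording that 25% yields about 45. Randomizing 64 would make the sum correct at 25%. Even so, under the same independence assumption, 64 would still fall short of 48 about 43% of the time without replacement (1 − 0.567), so a working replacement rule is needed either way.

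**Conclusion.** The plan is wrong as written. At its own 25% drop-out, 60 randomized give 45 completers, 3 below the stated minimum; 60 supports 20%. The 8.9 trigger is reached at 16 losses, three later than the point (13) at which the minimum is lost, and it is not reconciled with the unconditional rule in 5.2.3 and SAP 3.5.1. The arithmetic needs no assumption beyond taking the rate as a fraction of those randomized. If missed data and problematic subjects are losses on top of the 25%, the shortfall is larger; the plan does not quantify them.

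The 77% chance of fewer than 48 completers, including 34% for 13 to 15 losses, rests on independent drop-out at 25% and no replacement. The fall in power from 90.1% to 88.3% rests on the inferred basis for the 48; if 18.62 is already the SD of the paired difference, the fall is from 99.4% to 99.1%. The correction should be made, but the validity of the trial does not hang on it.

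**What to change.** Keep 60 and amend protocol 8.9 and SAP 3.3 together:

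1. Either give the attrition that 60 supports as about 20%, or state that 25% attrition is expected to leave about 45 completers. If the second wording is used, present 48 as a target to be met through replacement.
2. Drop the 25% trigger. Allow replacement to be considered once the number of subjects who have completed, or can still complete, all five treatment periods falls below 48, that is, at more than 12 losses of 60.
3. Cross-refer to protocol 5.2.3 and SAP 3.5.1 so that a single replacement rule applies, and use the same wording for the target of 48 in the synopsis.

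The trigger should not be a count of the Modified Completer population. Its second exclusion criterion compares a subject's placebo and positive-control Emax, which needs treatment codes and outcome data, while under protocol 5.2.4 "the randomization will remain blinded until all the CRFs have been approved and signed" in the Treatment phase. A completion count needs neither. It does not by itself guarantee 48 analysable subjects after exclusions for missing or unreliable data, and the text should say so.

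The cost is two sentences and a cross-reference in each document, with the protocol change submitted to the IRB as protocol 12.2 requires. Losses of 13 to 15 would mean about 1 to 3 replacements, more if replacements also drop out. Protocol 5.2.3 and SAP 3.5.1 already permit these.
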